## Glossary of terms

Additional treatment	Medicinal products that may be used during the clinical trial as described in the protocol, but not as an investigational medicinal product (e.g. any background therapy)
Assessment	A procedure used to generate data required by the study
Biologic Samples	A biological specimen including, for example, blood (plasma, serum), saliva, tissue, urine, stool, etc. taken from a study participant
Comprehensive Standard of Care (SoC)	Comprehensive SoC includes initial hospitalization and pharmacological SoC (antidepressant or antidepressant plus augmentation therapy)
Control drug	A study drug (active or placebo) used as a comparator to reduce assessment bias, preserve blinding of investigational drug, assess internal study validity, and/or evaluate comparative effects of the investigational drug
Dosage	Dose of the study treatment given to the participant in a time unit (e.g. 100 mg once a day, 75 mg twice a day)
Electronic Data Capture (EDC)	Electronic data capture (EDC) is the electronic acquisition of clinical study data using data collection systems, such as Web-based applications, interactive voice response systems and clinical laboratory interfaces. EDC includes the use of Electronic Case Report Forms (eCRFs) which are used to capture data transcribed from paper source forms used at the point of care
End of the clinical trial	The end of the clinical trial is defined as the last visit of the last participant or at a later point in time as defined by the protocol
Enrollment	Point/time of participant entry into the study at which informed consent must be obtained
Estimand	A precise description of the treatment effect reflecting the clinical question posed by the trial objective. It summarizes at a population-level what the outcomes would be in the same patients under different treatment conditions being compared. Attributes of an estimand include the population, variable (or endpoint) and treatment of interest, as well as the specification of how the remaining intercurrent events are addressed and a population-level summary for the variable.
eSource	eSource Direct Data Entry refers to the capture of clinical study data electronically, at the point of care. eSource Platform/Applications combines source documents and case report forms (eCRFs) into one application, allowing for the real time collection of clinical trial information to sponsors and other oversight authorities, as appropriate.

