Study treatment	Any drug or combination of drugs or intervention administered to the study participants as part of the required study procedures; includes investigational drug(s), control(s) or background therapy
Study treatment discontinuation	When the participant permanently stops taking any of the study drug(s) prior to the defined study treatment completion date (if any) for any reason; may or may not also be the point/time of study discontinuation
Treatment arm/group	A treatment arm/group defines the dose and regimen or the combination, and may consist of 1 or more cohorts.
Treatment of interest	The treatment of interest and, as appropriate, the alternative treatment to which comparison will be made. These might be individual interventions, combinations of interventions administered concurrently, e.g. as add-on to standard of care, or might consist of an overall regimen involving a complex sequence of interventions. This is the treatment of interest used in describing the related clinical question of interest, which might or might not be the same as the study treatment.
Variable (or endpoint)	The variable (or endpoint) to be obtained for each participant that is required to address the clinical question. The specification of the variable might include whether the participant experiences an intercurrent event.
Withdrawal of study consent (WoC)	Withdrawal of consent from the study occurs only when a participant does not want to participate in the study any longer and does not allow any further collection of personal data

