## 6 Treatment

### 6.1 Study treatment

Study treatment consists of MIJ821 or placebo in combination with pharmacological SoC.

MIJ821 20 mg will be centrally supplied as lyophilized powder in vials (pharmaceutical form). This will be reconstituted with 0.9% sodium chloride to obtain the solution for infusion for all MIJ821 doses. Placebo will consist of 0.9% sodium chloride infusion bag supplied by the site.

The first infusion of study treatment (Day 1) must be administered while the participant is hospitalized. All subsequent administrations may be performed either under hospitalization or as an outpatient in the clinic, at investigator's discretion.

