## **6.2 Other treatment(s)**

### **6.2.1 Concomitant therapy**

All participants must receive pharmacological antidepressant therapy during the Core Treatment Period and 52 weeks Extension Period. Pharmacological treatment may include an antidepressant, or antidepressant plus augmentation therapy (e.g. antipsychotics, lithium, etc). Dosage titration or adjustments of standard-of-care antidepressant treatment occurring during the first 2 weeks of double-blind treatment are allowed, if needed, with dosages maintained thereafter during the Core period.

Psychotherapy will also be allowed and any change must be appropriately documented in the source records and CRF.

Each concomitant drug must be individually assessed against all exclusion criteria/prohibited medication.

During the Extension Period, pharmacological antidepressant therapy can be modified only for non responders or participants who did not achieve remission (see [Section 3.2](#) for more details).

Those participants, who are classified as a responder or remitter at the End of the Core Period must maintain a stable SoC (see [Section 3.2](#) for more details). In case of a relapse, the SoC pharmacological treatment can be adjusted, if needed, during the first 2 weeks of retreatment. Participants may or may not be hospitalized for the treatment of relapse (as per clinical judgment and local practices).

Participants who are responder or remitter at the End of the Core Period, and relapse during the Extension Period but do not meet the weight requirements of 50-120kg (inclusive) to be retreated in case of relapse, may change their SoC, as required, and should discontinue the Extension as defined in [Section 3.3](#) Follow-up Duration.

All medications, procedures, and significant non-drug therapies (including physical therapy and blood transfusions) administered after the participant was enrolled into the study must be recorded on the appropriate Case Report Forms (CRFs).

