## **9 Study discontinuation and completion**

### **9.1 Discontinuation and completion**

#### **9.1.1 Study treatment discontinuation and study discontinuation**

Discontinuation of study treatment for a participant occurs when study treatment is stopped earlier than the protocol-planned duration. Discontinuation of study treatment can be initiated by either the participant or the investigator.

Discontinuation of study treatment may or may not include study drug infusion interruption, i.e. shortening of the infusion to less than 40 minutes. If the duration of an infusion is shortened, the next planned infusion should be planned to be administered for the full 40 minutes. If there is a concern that the participant cannot tolerate the full duration of the infusion the investigator should consider permanent discontinuation of study treatment.

The investigator must discontinue study treatment for a given participant if, he/she believes that continuation would negatively impact the participant's well-being.

Study treatment must be discontinued under the following circumstances:

- Participant/guardian decision
- Pregnancy
- Use of prohibited treatment as per recommendations in the prohibited treatment [Section 6.2.2](#)
- Any situation in which study participation might result in a safety risk to the participant
- Following emergency unblinding
- Severe hypersensitivity reaction such as anaphylaxis
- Adverse events (including AESI, see [Section 10.2.5](#)), abnormal laboratory values or abnormal test result that indicate a safety risk to the participant
- Lack of study treatment effect based on Investigator's judgement
- Patients meeting the discontinuation criteria for liver laboratory triggers or renal alert criteria as defined in [Table 16-4](#) and [Table 16-5](#)

- Study treatment should also be discontinued for any one of the following treatment-emergent events:
  - Absolute QTcF > 500 msec, confirmed by repeat ECG measurements
  - Resting heart rate < 30 or > 120 bpm
  - QRS > 120 msec and increase > 25% from Baseline (Day 1)
  - Sustained ventricular tachycardia lasting 30 sec or more, ventricular fibrillation, or any hemodynamically compromising cardiac arrhythmia
  - New complete heart block (Grade III AV block) or Second degree AV block Mobitz type II

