## **10 Safety monitoring and reporting**

### **10.1 Definition of adverse events and reporting requirements**

#### **10.1.1 Adverse events**

An adverse event (AE) is any untoward medical occurrence (e.g. any unfavorable and unintended sign [including abnormal laboratory findings], symptom or disease) in a clinical investigation participant after providing written informed consent for participation in the study. Therefore, an AE may or may not be temporally or causally associated with the use of a medicinal (investigational) product.

The investigator has the responsibility for managing the safety of individual participant and identifying adverse events.

Novartis qualified medical personnel will be readily available to advise on trial related medical questions or problems.

The occurrence of adverse events must be sought by non-directive questioning of the participant at each visit during the study. Adverse events also may be detected when they are volunteered by the participant during or between visits or through physical examination findings, laboratory test findings, or other assessments or reports [REDACTED]

Adverse events must be recorded under the signs, symptoms, or diagnosis associated with them, accompanied by the following information (as far as possible) (if the event is serious refer to [Section 10.1.2](#)):

1. The severity grade
  - mild: usually transient in nature and generally not interfering with normal activities
  - moderate: sufficiently discomforting to interfere with normal activities
  - severe: prevents normal activities
2. In relationship to the study treatment. If the event is due to lack of efficacy or progression of underlying illness (i.e. progression of MDD) the assessment of causality will usually be 'Not suspected.' The rationale for this guidance is that the symptoms of a lack of efficacy or progression of underlying illness are not caused by the trial drug, they happen in spite of its administration and/or both lack of efficacy and progression of underlying disease can only be evaluated meaningfully by an analysis of cohorts, not on a single participant
3. Its duration (start and end dates) or if the event is ongoing, an outcome of not recovered/not resolved must be reported
4. Whether it constitutes an SAE (see [Section 10.1.2](#) for definition of SAE) and which seriousness criteria have been met
5. Action taken regarding with study treatment.

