2.1.1 General definitions

Study drug (treatment)

Study drug (treatment) referred in this document will be MIJ821 or Placebo.

Randomization (Enrollment) Date

Randomization (Enrollment) Date is the date on which a participant is assigned to one of the treatments through IRT in Core Period.

Date of first dose

The date of first dose is the date on which a participant is administered the first infusion of study drug, which maybe on the same day or after the randomization date. For participants who are randomized but never dosed with double-blind study drug after randomization, the date of first dose is considered missing.

Date of last dose

The date of last dose is the latest infusion date throughout study, including Extension Period for participants who take retreatment for relapse.

Day 1

Day 1 is defined as the first dose date. For participants who are randomized but not dosed after randomization, the Study Day 1 is defined as the date of randomization.

Study day

Study Day is defined as the number of days from Study Day 1.

Before Study Day 1:

Study Day = (Date of Interest – Date of Study Day 1)

On or after Study Day 1:

Study Day = (Date of Interest – Date of Study Day 1) + 1

Therefore the day prior to Study Day 1 is -1.

Day(s) since start of retreatment is defined as the number of days from the first dose date of retreatment. It will be calculated for assessments performed during retreatment period by

Date of interest – Date of first dose of retreatment + 1

Baseline

A baseline value refers to the last evaluable measurement prior to the first dose, irrespective of re-screening. In this case, baseline values will be the values obtained predose on first dosing day or on an earlier visit (scheduled or unscheduled) which is the closest to the first dosing day, if the assessment was not done on the first dosing day. In case of multiple assessments on the same day, the last valid one will be considered.

Baseline of Retreatment

For participant who take retreatment during Extension Period, the baseline for retreatment assessments will be the last evaluable measurement prior to the first dose of retreatment. It will be the measurement obtained predose on the first day of retreatment, or the last valid assessment which is closest to start of retreatment.

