2.6.1 Adverse events (AEs)

Treatment-Emergent Adverse Events (TEAEs) are defined as adverse events starting or worsening after the first dose of study medication and up to 2 weeks post the last dose. For relapsed participants who receive retreatment of MIJ821 in Extension Period, adverse events starting after 2 weeks post the last dose of Core Period up to the start of retreatment will not be counted as TEAEs. The missing onset date of AE will be imputed before identify the TEAE (see imputation rule in [Appendix 5.1.1](#))

The Medical Dictionary for Regulatory Activities (MedDRA) version 24.0 or later will be used to code Adverse Event (AE) to a SOC and a PT.

TEAEs will be analyzed separately for Core Period and Retreatment Period:

- The summary of TEAEs in Core Period (up to 2 weeks post the last dose) will be based on SAF
- The summary of TEAEs in Retreatment Period (up to 2 weeks post the last dose of retreatment) will be based on RTS

The number (and percentage) of participants with TEAEs will be summarized by following approach as defined in [Table 2-7](#), in terms of all TEAEs, Treatment-Emergent Serious Adverse Events (TESAEs), TEAEs leading to treatment discontinuation, treatment-related TEAEs or TESAEs and death:

- by treatment, primary system organ class and preferred term
- by treatment, primary system organ class, preferred term and maximum severity
- by treatment, Standardized MedDRA Query (SMQ) and preferred term
- by treatment, preferred term with most frequent (incidence rate $\geq 5\%$)

Table 2-7 AE Summaries of Subject Incidence

Category	by SOC and PT	by SOC, PT and maximum severity	by most frequent PT (≥ 5%)
All TEAEs	Y	Y	Y
TESAEs	Y		
AEs leading to treatment discontinuation	Y		
Treatment-related TEAEs	Y		
Treatment-related SAEs	Y		
Deaths	Y		

For all AEs tables presented by SOC and PT (and grade), the SOC's will be presented in alphabetical order and PTs will be ordered within the SOC by decreasing order of frequency. AE tables by preferred term only will be sorted in descending order of frequency.

A participant with multiple adverse events within a primary system organ class is only counted once towards the total of the primary system organ class.

All AEs, deaths, SAEs and AEs leading to permanent study drug discontinuation will be listed separately.

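### The protocol's 'study treatment' formally includes the background antidepressant, so an event attributed to the antidepressant can be recorded as related and then reported by the SAP as related to MIJ821 or placebo

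*Protocol*

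**What the plan says.** Three places in the protocol put the background antidepressant (SoC) inside 'study treatment'. Section 6.1 reads "Study treatment consists of MIJ821 or placebo in combination with pharmacological SoC". The glossary entry says the term "includes investigational drug(s), control(s) or background therapy". The study treatment row of the protocol summary lists pharmacological SoC beside MIJ821 and placebo.

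Section 10.1.1, item 2, requires each adverse event to be judged "In relationship to the study treatment". It describes no separate judgement for the antidepressant. Protocol Section 12.5.2 then promises summaries of events related to 'study medication', a term the glossary does not define.

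The SAP is narrower. Section 2.1.1 says "Study drug (treatment) referred in this document will be MIJ821 or Placebo". Section 2.6.1 summarises "treatment-related TEAEs or TESAEs and death", and Table 2-7 has rows for treatment-related TEAEs and treatment-related SAEs. Table 2-8 adds disclosure counts of SAEs, and of deaths, causally related to treatment. SAP Section 4 lists no change to the protocol's analyses.

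The antidepressant is given in every arm. Section 6.2.1 states: "All participants must receive pharmacological antidepressant therapy during the Core Treatment Period and 52 weeks Extension Period".

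**The concern.** The causality question and the table that reports its answer use the same word with different stated meanings. An investigator who follows Section 6.1 and the glossary would answer yes for a side effect of an antidepressant. A reader who follows SAP Section 2.1.1 would take that yes as a statement about MIJ821 or saline. If only one judgement is recorded per event, the SAP cannot separate the components afterwards.

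The situation can easily arise. Section 3.1 allows the antidepressant to be started or adjusted during Screening, and Section 3.2 allows titration in the first two weeks of the Core Period. The TEAE window runs from the first infusion to two weeks after the last, so new antidepressant effects can fall inside it.

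At stake is what the related-event tables mean, including the related SAE and death counts prepared for public disclosure. So are the steps in Section 10.1.3 that depend on an SAE being thought related to study treatment: the sponsor's urgent request for more information, a possible investigator notification, and SUSAR handling.

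**Working it through.** No figure in the plan bears on this point, so the check is a comparison of texts.

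**1. What does 'study treatment' mean where it is defined?** Section 6.1, the glossary entry and the protocol summary all include the antidepressant. The glossary is not consistent with itself: its entry for additional treatment covers products used in the trial "but not as an investigational medicinal product (e.g. any background therapy"). Section 6.2.1 handles the same drugs as concomitant therapy. The antidepressant thus carries three labels: study treatment, additional treatment and concomitant therapy.

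**2. What does it mean where it is used?** Often only the infusion:
- Section 6.1 goes on to speak of the first infusion of study treatment.
- Section 6.7 and the text under Table 6-3 put MIJ821 or placebo in brackets after the term.
- Section 6.7.1.1 has study treatment received and stored by unblinded staff, which does not fit a locally prescribed antidepressant.

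**3. What does it mean in the causality item?** This is unclear. Item 2 names study treatment, but its rationale on lack of efficacy speaks of the trial drug. Item 5, on action taken, offers only infusion actions. No sentence says which component the judgement refers to.

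**4. What does the SAP do with the answer?** It applies the narrow definition and tabulates by arm. It does not say which protocol item feeds the tables, or that the protocol's formal definition is wider.

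**5. Which outputs depend on the answer?**

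| Output | Uses relatedness? |
|---|---|
| Primary analysis, MADRS change at 24 hours | No |
| Secondary safety endpoint: number and severity of TEAEs, including AESIs | No |
| Table 2-7: all TEAEs, TESAEs, discontinuations, deaths | No |
| AESI summaries, SAP 2.6.1.1 | No |
| Table 2-7: treatment-related TEAEs and SAEs | Yes |
| Table 2-8: causally related SAEs and deaths | Yes |
| Protocol 10.1.3: first report of an SAE to the sponsor | No, all SAEs are reported |
| Protocol 10.1.3: follow-up of SAEs thought related | Yes |

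**6. In which direction, and how much?** Every arm takes the antidepressant and the judging investigator is blinded. Misplaced attribution can therefore occur in any arm, saline included, and would not by itself favour one. It would add a shared background to the related counts. The documents give neither a rate of antidepressant-attributed events nor the share that sites would record as related, so no size can be calculated.

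**The case against.** The strongest reply is that investigators will understand study treatment as the infusion. The operative text in steps 2 and 3 above supports this, and the AE form, which is not among the documents, may already name the infusion. This reply stands against the flat statement that antidepressant side effects are counted as drug-related, which a reader might infer from Section 6.1 alone. It does not remove the ambiguity. The formal definitions say the opposite, and sites are entitled to follow either.

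A second reply is that any such background falls on all arms, is compared with concurrent placebo, and is present in the all-cause tables anyway. That is correct and limits the harm. It does not make the related-event tables mean what the SAP says they mean.

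Three stronger readings are tempting and are not supported:
- *The Safety Set takes in people who received only the antidepressant.* SAP Table 5-2 excludes anyone who took no double-blind study drug, and protocol Section 12.1 defines treatment received by reference to the randomised assignment.
- *The mandatory stops in Section 9.1.1 ("Study treatment must be discontinued under the following circumstances") also stop the antidepressant and so contradict Section 6.2.1.* Section 9.1.1 itself explains discontinuation as there being no more infusions to come, and has it registered in the IRT.
- *Related-event counts drive dose selection.* Protocol Sections 4.4 and 12.7 refer to safety in general, and the secondary safety endpoint does not use relatedness.

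**Conclusion.** The point holds as a conflict between stated definitions with a limited reach. By the protocol's formal wording, an event attributed to the antidepressant is related to study treatment; by the SAP's wording, the same record is reported as related to MIJ821 or placebo. Such events can be misreported in this way in any arm. Whether they are depends on how sites read the term and how the AE form words the question, and neither can be seen from the documents.

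The exposed outputs are the treatment-related rows of SAP Table 2-7, the causally related rows of Table 2-8, and the relatedness-dependent steps of SAE reporting. The size is unknown, and any percentage offered would rest wholly on assumed rates. The efficacy conclusions and the all-cause safety picture are not at risk. The correction is still worth making, because it is cheap and an attribution recorded only once at site cannot be split later.

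**What to change.** - In protocol Section 10.1.1, item 2, and on the AE form, state that causality is judged against the investigational infusion (MIJ821 or placebo). Capture causality to the antidepressant as a separate item.
- In SAP Section 2.6.1 and Tables 2-7 and 2-8, state that the related-event counts use the first item only.
- Align the term in protocol Section 6.1, the glossary, the protocol summary and Section 12.5.2 with SAP Section 2.1.1, and give the antidepressant one label throughout.
- Where the stopping and contraception text uses the term, reconcile the passages so that each says which component it means. No view is taken here on what those rules should be.

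The cost is wording changes in both documents and one extra item per adverse event. Fewer events may be labelled related. For events already recorded under a single item, the most the tables can do is carry a footnote naming what the form asked causality to be judged against.
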